#### 16.43 Exploratory Outcomes Analyses

- 16.431 To evaluate the correlation of MRD assessment between blood and bone marrow, patients will be categorized as positive vs. negative MRD for each measure. The number of patients who have agreement between the 2 measures (both positive or both negative) will be assessed.
- 16.432 To evaluate the correlation of MRD assessment between flow cytometry (MPF) and NGS, patients will be categorized as positive vs. negative MRD for each measure. The number of patients who have agreement between the 2 measures (both positive or both negative) will be assessed.
- 16.433 Immune repertoire profiling (Section 1.74) will be assessed as continuous variables and their mutual change over time as assessed on the pre-specified time points will be correlated with response category to the treatment.
- 16.434 ADCP and ADCC (Section 1.75) will be assessed as continuous variables and their mutual change over time as assessed on the pre-specified time points will be correlated with response category to the treatment

#### 16.5 Data and Safety Monitoring:

- 16.51 The principal investigator(s) and the study statistician will review the study at least twice a year to identify accrual, adverse event, and any endpoint problems that might be developing. The Mayo Clinic Cancer Center (MCCC) Data Safety Monitoring Board (DSMB) is responsible for reviewing accrual and safety data for this trial at least twice a year, based on reports provided by the MCCC Statistical Office.

#### 16.52 Adverse Event Stopping Rules:

The stopping rules specified below are based on the knowledge available at study development. We note that the Adverse Event Stopping Rule may be adjusted in the event of either (1) the study re-opening to accrual or (2) at any time during the conduct of the trial and in consideration of newly acquired information regarding the adverse event profile of the treatment(s) under investigation. The study team may choose to suspend accrual because of unexpected adverse event profiles that have not crossed the specified rule below.

Accrual will be temporarily suspended to this study if at any time we observe events considered at least possibly related to study treatment (i.e. an adverse event with attribute specified as “possible,” “probable,” or “definite”) that satisfy one of the following:

- If 5 or more patients in the first 15 treated patients experience a grade 4 or higher non-hematologic adverse event at least possibly related to treatment.
- If after the first 15 patients have been treated, 30% of all patients experience a grade 4 or higher non-hematologic adverse event at least possibly related to treatment.

We note that we will review grade 4 and 5 adverse events deemed “unrelated” or “unlikely to be related”, to verify their attribution and to monitor the emergence of a previously unrecognized treatment-related adverse event.

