**unless otherwise specified ← ←**

CTCAE System/Organ/Class (SOC)	ADVERSE EVENT	AGENT	ACTION**
Investigations	Neutrophil count decreased Grade 4 lasting >7 days	Daratumumab	Hold (Day 1) or Omit (Days 8, 15, or 22) Daratumumab ** until recovery to Grade ≤2 or baseline May restart at same dose at the next planned dosing date.
	Platelet count decreased Grade ≥3 with bleeding		
Blood and lymphatic system disorders	Febrile neutropenia ≥Grade 3		Hold (Day 1) or Omit (Days 8, 15, or 22) Daratumumab ** until recovery to Grade ≤2 or baseline May restart at same dose at the next planned dosing date.
	Neutropenia with infection, of any grade		
Gastrointestinal disorders	Nausea Grade 2 (if persistent for >7 days despite optimal antiemetic therapy)		Hold (Day 1) or Omit (Days 8, 15, or 22) Daratumumab ** until recovery to Grade ≤1 or baseline May restart at same dose at the next planned dosing date.
	Vomiting ≥Grade 3 (if persistent for >7 days despite optimal antiemetic therapy)		
	Diarrhea ≥Grade 3 (if persistent for >7 days despite optimal anti-diarrheal therapy)		
Other (Non-hematologic)****	Any other Grade 4 AE or any unmanageable Grade 3 AE that was present at baseline or lasts for >7 days after the last administration of daratumumab		Hold (Day 1) or Omit (Days 8, 15, or 22) Daratumumab ** until recovery to Grade ≤1 or baseline May restart at same dose at the next planned dosing date.

Additional Adverse Events:

\*\* If Daratumumab is omitted in the middle of the cycle and the toxicity resolves, patient can re-start the drug but the days of drug treatment missed do not need to be caught-up and can be omitted in order to maintain the cycle schedule.

- Dose omission: Daratumumab may be omitted for adverse event considerations for a maximum of 28 consecutive days during Consolidation 1 (Cycle 1-2 or 1-4, as the case may be for that patient). Patients on maintenance therapy may be continued on treatment with single-agent daratumumab or lenalidomide in case the other agent has to be permanently discontinued in absence of disease progression. If a patient on maintenance treatment must discontinue both,

lenalidomide and daratumumab, they should be removed from the protocol therapy and proceed to event monitoring.

- If multiple adverse events are seen, administer dose based on the greatest reduction required by any single adverse event observed.

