**10.52 Death**

**Note: A death on study requires both routine and expedited reporting regardless of causality, unless as noted below. Attribution to treatment or other cause must be provided.**

Any death occurring within 30 days of the last dose, regardless of attribution to an agent/intervention under an IND/IDE requires expedited reporting within 24-hours.

Any death occurring greater than 30 days with an attribution of possible, probable, or definite to an agent/intervention under an IND/IDE requires expedited reporting within 24-hours.

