## 11.6 Criteria for engraftment (for hematopoietic stem cell transplant studies only)

Engraftment is defined as:

- The first day of three consecutive days on which the absolute neutrophil count (ANC)  $>500/\text{mm}^3$  and
- The first of three consecutive days with an untransfused platelet count  $>20,000/\text{mm}^3$ .

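### The only mandatory numerical toxicity trigger (16.52) gives related deaths no weight of their own and can leave related deaths coded to hematologic terms uncounted

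*Combined protocol and SAP*

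**What the plan says.** Section 16.52 sets two triggers. In the first 15 treated patients: "If 5 or more patients in the first 15 treated patients experience a grade 4 or higher non-hematologic adverse event at least possibly related". Thereafter: "If after the first 15 patients have been treated, 30% of all patients experience a grade 4 or higher non-hematologic adverse event". The consequence is mandatory and applies throughout: "Accrual will be temporarily suspended to this study if at any time we observe events considered at least possibly related to study treatment". Grade 5 lies inside the Grade 4-or-higher class, and no separate line deals with deaths. The term non-hematologic is not defined.

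Febrile neutropenia ("Febrile neutropenia ≥Grade 3") stands under blood and lymphatic system disorders in the dose-modification tables of 8.2 and 8.3. Section 15.15 places febrile neutropenia, neutropenic sepsis and neutropenic infection under the same kind of heading.

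Other provisions touch on deaths or toxicity without a threshold:

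- 16.52 adds a discretionary power: "The study team may choose to suspend accrual because of unexpected adverse event profiles that have not crossed the specified rule below". It also allows the rule to be adjusted during the trial and has Grade 4 and 5 events judged unrelated re-examined.
- 10.52 requires 24-hour reporting: "Any death occurring within 30 days of the last dose, regardless of attribution". No accrual action follows from the report.
- 16.51 requires the investigators and statistician, and the DSMB, to review at least twice a year.
- 16.12, 16.314, 16.33 and 13.4 mention undue toxicity, adverse events or safety concerns as grounds for action.

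Section 16.314 cites the adverse event stopping rule as part of the reason for not halting accrual at the interim analysis.

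**The concern.** Leaving out hematologic events is sensible for expected cytopenias, which would otherwise trip the rule on ordinary transplant and lenalidomide toxicity. The same exclusion, read literally, also removes deaths coded to a hematologic term. The pooling of Grades 4 and 5 sets the tolerance for deaths at the tolerance for Grade 4 events, about one patient in three early on and 30% later.

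Section 16.314 leans on this rule as an ethical safeguard for continuous accrual, so its response to treatment-related death matters. At the planned 2 evaluable patients per month (16.13), about 2 × 6 = 12 patients could enter between DSMB reviews held at the minimum frequency of twice a year.

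**Working it through.** The documents give no operating characteristics for the safety rule, so there is no stated figure to reproduce.

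**Inputs.** Boundary of 5 patients up to n = 15, then 30% of n (16.52). Maximum of 45 evaluable patients (16.12). The true related-death rate p is assumed, from 5% to 30%, because the documents give none. Deaths are taken as the only qualifying events and all are taken to count.

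**Boundary in patients.** For n above 15 it is 0.30n rounded up: 5 at n = 16, 6 at n = 17 to 20, 9 at n = 30, 12 at n = 40, 13 at n = 41 to 43, and 14 at n = 44 and 45.

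**Four deaths in the first 15.** 4/15 = 26.7%, against 5/15 = 33.3%. Four is also below every later boundary, the smallest of which is 5. Four deaths alone therefore never cross. One further patient with a related Grade 4 non-hematologic event among the first 15 makes 5, and the rule is crossed.

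**Chance of crossing in the first 15.** This is the sum over k = 5 to 15 of C(15,k) p^k (1−p)^(15−k).

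**Chance of ever crossing by 45.** An exact patient-by-patient recursion carries the probability of each count still below the boundary from n to n + 1 and adds up the probability that reaches it.

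| Assumed related-death rate | Crosses in first 15 | Crosses by 45 |
|---|---|---|
| 5% | 0.001 | 0.001 |
| 10% | 0.013 | 0.022 |
| 15% | 0.062 | 0.110 |
| 20% | 0.164 | 0.297 |
| 30% | 0.485 | 0.770 |

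**Deaths coded to a hematologic term.** If non-hematologic is read by system organ class, such deaths add nothing to the count at any rate. If a fatal infection in a neutropenic patient is coded under infections, where 15.15 lists sepsis and pneumonia, it counts. The same clinical course can count or not count depending on the term chosen.

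**Illustration of a separate death count** (2 in the first 15, then at least 10% of treated patients; the boundary is 2 to n = 20, 3 to n = 30, 4 to n = 40 and 5 to n = 45). The same recursion gives these pause probabilities by 45:

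| Assumed related-death rate | Pauses by 45 |
|---|---|
| 1% | 0.02 |
| 2% | 0.07 |
| 3% | 0.14 |
| 5% | 0.32 |
| 10% | 0.74 |
| 20% | 0.99 |

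**The case against.** The strongest reply is that pooling Grades 4 and 5 is a legitimate design choice that no other passage contradicts, and that the numerical rule is not the only protection. The team can suspend below the boundary, deaths within 30 days of the last dose are reported within 24 hours, the DSMB reviews safety, and 16.33 and 13.4 allow the study to be stopped. The calculation also isolates deaths, whereas other related Grade 4 non-hematologic events would bring the count closer to the boundary.

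Much of this stands, and it rules out several stronger readings:

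- A reader might infer that accrual would continue after four related deaths. The documents show only that suspension would not be required, and only if no other qualifying event occurred.
- A reader might infer that any number of fatal febrile neutropenias count as zero. That depends on an undefined term. The protocol files neutrophil and platelet decreases under investigations, so organ class cannot be its whole dividing line between hematologic and non-hematologic.
- A reader might infer that any total below 30% at the end, such as 13 deaths in 45 patients, escapes. The rule applies at any time, and 13 events by patient 43 cross it. Counting all orderings of 13 events among 45 patients, about 88% cross somewhere.
- A reader might infer that failed engraftment is an excluded hematologic event. Section 11.6 ("Criteria for engraftment (for hematopoietic stem cell transplant studies only") defines engraftment by neutrophil and platelet recovery, but nowhere is its failure named or classed as an adverse event, so the documents do not support making it a trigger.

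The reply does not supply a mandatory response to related deaths as such. The other routes are discretionary or carry no threshold, and the discretionary clause in 16.52 speaks of unexpected profiles, while febrile neutropenia and neutropenic sepsis are listed toxicities.

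**Conclusion.** The point holds in limited form. The only mandatory numerical safety trigger gives related deaths no separate weight and, as worded, can leave those coded to febrile neutropenia or neutropenic sepsis uncounted. With deaths as the only qualifying events, and all of them counted, it triggers by 45 patients with probability 0.02 at a 10% related-death rate and 0.30 at 20%. These rates are assumptions, and any other qualifying events would raise the probabilities. This is a gap in a rule that 16.314 relies on, not evidence that deaths would go unreported or unreviewed. The efficacy decision rule is unaffected.

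**What to change.** In 16.52, state that every Grade 5 event at least possibly related to study treatment counts toward both triggers regardless of system organ class. This is one clause, and 16.52 already provides for adjusting the rule. The cost is a slightly higher chance of a temporary pause. As a guide to scale, if deaths now excluded raised the qualifying rate from 10% to 15%, the chance of crossing by 45 would go from 0.02 to 0.11.

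Optional, for the sponsor to decide:

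- A separate related-death count that prompts DSMB review, with the threshold and its operating characteristics chosen and stated by the sponsor. The illustrative boundary above shows the trade-off: it pauses with probability 0.02 to 0.07 at true rates of 1 to 2%, but 0.14 at 3% and 0.32 at 5%. Whether that is acceptable depends on an expected rate that the documents do not give.
- A descriptive summary in 16.42 of engraftment by the 11.6 definition, which Section 16 does not use at present. The cost is abstracting the dates from transplant blood counts.

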#### 16.6 Results Reporting on ClinicalTrials.gov

At study activation, this study will have been registered within the “ClinicalTrials.gov” website. The Primary and Secondary Endpoints along with other required information for this study will be reported on [www.ClinicalTrials.gov](http://www.ClinicalTrials.gov). For purposes of timing of the Results Reporting, the initial estimated completion date for the Primary Endpoint of this study is 3 years after the study opens to accrual. The definition of “Primary Endpoint Completion Date” (PECD) for this study is at the time all patients registered have been followed at least through the day 100 post ASCT visit (approximately 8 months) or have discontinued study treatment prior to ASCT.

#### 16.7 Inclusion of Women and Minorities:

16.71 This study will be available to all eligible patients, regardless of race, gender, or ethnic origin.

16.72 There is no information currently available regarding differential effects of this regimen in subsets defined by race, gender, or ethnicity, and there is no reason to expect such differences to exist. Therefore, although the planned analysis will, as always, look for differences in treatment effect based on racial and gender groupings, the sample size is not increased in order to provide additional power for subset analyses.

16.73 The geographical region served by MCCC has a population which includes approximately 5% minorities. Based on prior MCCC studies involving similar disease sites, we expect about 5-7% of patients will be classified as minorities by race and about 40% of patients will be women. Expected sizes of racial by gender subsets are shown in the following table:

## Accrual Estimates by Gender/Ethnicity/Race

Accrual Targets			
Ethnic Category	Sex/Gender		
	Females	Males	Total
Hispanic or Latino	0	1	1
Not Hispanic or Latino	20	29	49
Ethnic Category: Total of all subjects	20	30	50
Racial Category			
American Indian or Alaskan Native	0	0	0
Asian	0	0	0
Black or African American	1	1	2
Native Hawaiian or other Pacific Islander	0	0	0
White	19	29	48
Racial Category: Total of all subjects	20	30	50

**Ethnic Categories:** **Hispanic or Latino** – a person of Cuban, Mexican, Puerto Rican, South or Central American, or other Spanish culture or origin, regardless of race. The term “Spanish origin” can also be used in addition to “Hispanic or Latino.”  
**Not Hispanic or Latino**

**Racial Categories:** **American Indian or Alaskan Native** – a person having origins in any of the original peoples of North, Central, or South America, and who maintains tribal affiliations or community attachment.  
**Asian** – a person having origins in any of the original peoples of the Far East, Southeast Asia, or the Indian subcontinent including, for example, Cambodia, China, India, Japan, Korea, Malaysia, Pakistan, the Philippine Islands, Thailand, and Vietnam. (Note: Individuals from the Philippine Islands have been recorded as Pacific Islanders in previous data collection strategies.)  
**Black or African American** – a person having origins in any of the black racial groups of Africa. Terms such as “Haitian” or “Negro” can be used in addition to “Black or African American.”  
**Native Hawaiian or other Pacific Islander** – a person having origins in any of the original peoples of Hawaii, Guam, Samoa, or other Pacific Islands.  
**White** – a person having origins in any of the original peoples of Europe, the Middle East, or North Africa.

## 17.0 Pathology Considerations/Tissue Biospecimens: None.

## 18.0 Records and Data Collection Procedures

### 18.1 Submission Timetable

Data submission instructions for this study can be found in the Data Submission Schedule.

### 18.2 Event monitoring

See [Section 4.2](#) and data submission table for the event monitoring/survival follow-up schedule.

### 18.3 CRF completion

This study will use Medidata Rave for remote data capture (rdc) of all study data.

### 18.4 Site responsibilities

Each site will be responsible for insuring that all materials contain the patient's initials, MCCC registration number, and MCCC protocol number. Patient's name must be removed.

### 18.5 Supporting documentation

This study requires supporting documentation for diagnosis prior to study entry as well as for evidence of response to study therapy and progression after study therapy. For patients with any previous ASCT for MM, provide a clinic note including ASCT history or transplant records (E.g. central registry records) . Supporting documentation for diagnosis will include either a pathology report or a laboratory report demonstrating multiple myeloma (including SPEP, UPEP, FLC, Serum and Urine Immunofixation, Bone Marrow Biopsy and Aspirate, skeletal bone survey, PET scan, Plasma Cell Proliferation and Assessment and FISH). These reports should be uploaded into the Supporting Documentation: Baseline form within 14 days of registration.

For progression of disease prior to study entry, supporting documentation includes the evidence needed to determine the patient's progression prior to enrollment. These documents should be uploaded into the Supporting Documentation: Baseline form within 14 days of registration.

For response to treatment, supporting documentation may include SPEP, UPEP, FLC, Serum and Urine Immunofixation, Bone Marrow Biopsy and aspirate, skeletal bone survey, and PET scan. These documents should be uploaded into the Supporting Documentation form.

For patients who progress after study therapy supporting documentation may include any of the following: SPEP, UPEP, FLC, serum and urine immunofixation, bone marrow biopsy and aspirate, skeletal bone survey, and PET scan. These documents should be uploaded into the Supporting Documentation form.

### 18.6 Labelling of materials

Each site will be responsible for insuring that all materials contain the patient's initials, MCCC registration number, and MCCC protocol number. Patient's name must be removed.

### 18.7 Incomplete materials

Any data entered into a form will result in that form being marked as “received.” However, missing data will be flagged by edit checks in the database.

18.8 Overdue lists

A list of overdue materials is automatically available to each site at any time. The appropriate co-sponsor/participant will be responsible to obtain the overdue material.

18.9 Correction forms

If a correction is necessary the QAS will query the site. The query will be sent to the appropriate site to make the correction in the database and respond back to the QAS.

**19.0 Budget**

- 19.1 Costs charged to patient: All routine clinical care. Lenalidomide and daratumumab procurement.
- 19.2 Tests to be research funded: None.
- 19.3 Other budget concerns: Protocol administration, study coordinator time, data management, and statistical analysis efforts will be funded by the Division of Hematology-Oncology.

## Appendix I ECOG Performance Status Scale

### ECOG PERFORMANCE STATUS\*

#### Grade || ECOG

0	Fully active, able to carry on all pre-disease performance without restriction
1	Restricted in physically strenuous activity but ambulatory and able to carry out work of a light or sedentary nature, e.g., light house work, office work
2	Ambulatory and capable of all selfcare but unable to carry out any work activities. Up and about more than 50% of waking hours
3	Capable of only limited selfcare, confined to bed or chair more than 50% of waking hours.
4	Completely disabled. Cannot carry on any selfcare. Totally confined to bed or chair.
5	Dead

\*As published in Am. J. Clin. Oncol.:

The ECOG Performance Status is in the public domain therefore available for public use. To duplicate the scale, please cite the reference above and credit the Eastern Cooperative Oncology Group, Robert Comis M.D., Group Chair.

From [http://www.ecog.org/general/perf\\_stat.html](http://www.ecog.org/general/perf_stat.html)

**Appendix II Creatinine Clearance (CrCl) Calculation**Cockcroft-Gault Equation:

$$\text{Creatinine clearance for males} = \frac{(140 - \text{age})(\text{weight in kg})}{(72)(\text{serum creatinine in mg/dL})}$$

$$\text{Creatinine clearance for females} = \frac{(140 - \text{age})(\text{weight in kg})(0.85)}{(72)(\text{serum creatinine in mg/dL})}$$

### Appendix III New York Heart Association Classification of Congestive Heart Failure

NYHA Class	Symptoms
I	Cardiac disease, but no symptoms and no limitation in ordinary physical activity, e.g. no shortness of breath when walking, climbing stairs etc.
II	Mild symptoms (mild shortness of breath and/or angina) and slight limitation during ordinary activity.
III	Marked limitation in activity due to symptoms, even during less-than-ordinary activity, e.g. walking short distances (20–100 m). Comfortable only at rest.
IV	Severe limitations. Experiences symptoms even while at rest . Mostly bedbound patients.

*Adapted from Dolgin M, Association NYH, Fox AC, Gorlin R, Levin RI, New York Heart Association. Criteria Committee. Nomenclature and criteria for diagnosis of diseases of the heart and great vessels. 9th ed. Boston, MA: Lippincott Williams and Wilkins; March 1, 1994. Original source: Criteria Committee, New York Heart Association , Inc. Diseases of the Heart and Blood Vessels. Nomenclature and Criteria for diagnosis, 6th edition Boston, Little, Brown and Co. 1964, p 114.*

